## **8.2 Pharmacokinetic and Statistical Analyses**

Primary pharmacokinetic measures include  $T_{max}$ ,  $C_{max}$ ,  $AUC_{0-t}$ , and  $AUC_{0-inf}$ . Secondary pharmacokinetic measures include the ratio of  $AUC_{0-t}$  to  $AUC_{0-inf}$ ,  $T_{1/2}$ ,  $K_{el}$ ,  $Cl/F$  and  $V_d/F$ .

All evaluable subjects completing at least one treatment period will be included in the pharmacokinetic analysis.

Descriptive statistics will be used to summarize pretomanid plasma concentrations at each sampling time point and for derived plasma PK parameters, as applicable. Statistics include sample size (n), mean, SD, percentage coefficient of variation (%CV), geometric mean, median, minimum, and maximum.

For each participant, pretomanid plasma concentration-time data will be graphically presented. Similarly, graphs of the mean plasma concentration-time profiles and overlay graphs with combined individual plasma concentration-time profiles will be produced. Additionally, pharmacokinetic parameters may be explored graphically.

The bioavailability of 4 x 50 mg dispersible tablets relative to the 200-mg reference tablet will be determined separately for each panel using a mixed model with the log transformed PK parameter ( $C_{max}$ ,  $AUC_{0-t}$ , and  $AUC_{0-inf}$ ) as response variable; sequence, period, and treatment as fixed effects; and participant as random effect.

The effect of dose on the relative bioavailability of the dispersible tablet will be determined separately for each panel using the same model as above.

The effect of food on the relative bioavailability of pretomanid will be determined comparing, across panels, each formulation and dose taken after eating breakfast versus

Protocol Pa-824-CL-011 V1.0

the same formulation and dose taken in fasted conditions using a mixed model with the log transformed PK parameter as response variable; panel, sequence, period, treatment, and panel-by-treatment interaction as fixed effects; and participant as random effect.

The  $T_{max}$  of pretomanid for each of the formulations will be descriptively compared.

Other statistical models and/or population pharmacokinetic modelling may also be used for further data interpretation.

Pharmacokinetic calculations will be performed using appropriate software.

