## 6.10 Statistical Analyses of Pharmacokinetic Data

### 6.10.1 Relative Bioavailability

The bioavailability of 4 x 50 mg dispersible tablets (Treatment B) relative to the 200-mg reference tablet (Treatment A) will be determined separately for each panel using a mixed model with log transformed PK parameters ( $C_{max}$ ,  $AUC_{0-t}$ , and  $AUC_{0-inf}$ ) as response variable; sequence, period, and treatment as fixed effects; and subject as random effect. The effect of dose on the relative

QMD Ref: Worldwide-TMP-ST-006-4.0 Effective: 12Aug2019	Governing QMD: Worldwide-SOP-ST-001
Confidentiality Statement	
This document is the property of Worldwide Clinical Trials Inc. and may not be duplicated, copied, altered or removed from company without prior approval from Worldwide Quality Assurance or in compliance with Worldwide Standard Operating Procedures.	

Worldwide Clinical Trials Controlled Quality Management Document		
 WORLDWIDE CLINICAL TRIALS	Sponsor: Protocol Number:	TB Alliance Pa-824-CL-011
STATISTICAL ANALYSIS PLAN – PHASE 1		

bioavailability of the dispersible tablets (Treatments B, C, and D) will be determined separately for each panel using a power model (Smith, 2000) of the following general form,

$$\ln(\text{PK}) = \ln(\beta_0) + \beta_1 \cdot \ln(\text{Dose}) + \varepsilon,$$

Where

PK is the pharmacokinetic parameter tested (e.g.  $C_{\max}$  or AUC)

$\ln(\beta_0)$  is the y-intercept,

$\beta_1$  is the slope (a value of  $\beta_1 \approx 1$  indicates linearity), and

$\varepsilon$  is an error term

The estimate of  $\beta_1$  with the 90% CIs will be reported along with the dose range for proportionality.

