### 6.10.2 Food Effect

The effect of food on the relative bioavailability of pretomanid will be determined by comparing Panel 1 (Fed) to Panel 2 (Fasted) for each treatment using an ANOVA model with panel as the fixed effect. For informational purposes, the food effect will also be evaluated using the following ANOVA models:

- 1) Using data from the 4 x 50 mg dispersible tablets (Treatment B) and the 200-mg reference tablet (Treatment A) from both panels the ANOVA model will include panel, treatment, and the panel by treatment interaction term as fixed effects to determine if the food effect differs across the two treatments. A p-value equal to or smaller than 0.05 for the panel by treatment interaction term indicates that the food effect differs between the treatments. If the p-value is greater than 0.05 an ANOVA model with panel and treatment as the fixed effects will be used to determine the common food effect for Treatments A and B (Panel 1 vs Panel 2).
- 2) Using data from the dispersible tablets (Treatments B, C, and D) from both panels the ANOVA model will include panel, treatment, and the panel by treatment interaction term as fixed effects to determine if the food effect differs across the dispersible tablets. A p-value equal to or smaller than 0.05 for the panel by treatment interaction term indicates that the food effect differs among the dispersible tablets. If the p-value is greater than 0.05 an ANOVA model with panel and treatment as the fixed effects will be used to determine the common food effect for the dispersible tablets (Panel 1 vs Panel 2).

QMD Ref: Worldwide-TMP-ST-006-4.0 Effective: 12Aug2019	Governing QMD: Worldwide-SOP-ST-001
Confidentiality Statement	
This document is the property of Worldwide Clinical Trials Inc. and may not be duplicated, copied, altered or removed from company without prior approval from Worldwide Quality Assurance or in compliance with Worldwide Standard Operating Procedures.	

Worldwide Clinical Trials Controlled Quality Management Document		
 WORLDWIDE CLINICAL TRIALS	Sponsor: Protocol Number:	TB Alliance Pa-824-CL-011
STATISTICAL ANALYSIS PLAN – PHASE 1		

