## 7 CHANGES TO PLANNED PROTOCOL ANALYSIS

No changes to the planned analyses have been identified.

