14.4.3	Statistical Analysis of the Natural Log-Transformed Systemic Exposure of Pretomanid Comparing Test Treatment of Dispersible Tablet (Treatment B) to the Reference 200 mg Immediate Release Tablet (Panel 1)		
14.4.4	Statistical Analysis of the Natural Log-Transformed Systemic Exposure of Pretomanid Comparing Test Treatment of Dispersible Tablet (Treatment B) to the Reference 200 mg Immediate Release Tablet (Panel 2)		
14.4.5	Statistical Analysis of the Natural Log-Transformed Systemic Exposure of Pretomanid Among Treatments Comparing Panel 1 vs. Panel 2		
14.4.6	Assessment of Dose Effect on Relative Bioavailability of Dispersible Tablets (Treatments B, C, and D) (Panel 1)		
14.4.7	Assessment of Dose Effect on Relative Bioavailability of Dispersible Tablets (Treatments B, C, and D) (Panel 2)		
14.4.8	Assessment of Food Effect Across 200 mg Treatments (A and B) on Log-Transformed PK Parameters		
14.4.9	Assessment of Food Effect Across Dispersible-Tablet Treatments (B, C, and D) on Log-Transformed PK Parameters		

QMD Ref: Worldwide-TMP-ST-006-4.0 Effective: 12Aug2019	Governing QMD: Worldwide-SOP-ST-001
Confidentiality Statement	
This document is the property of Worldwide Clinical Trials Inc. and may not be duplicated, copied, altered or removed from company without prior approval from Worldwide Quality Assurance or in compliance with Worldwide Standard Operating Procedures.	

Worldwide Clinical Trials Controlled Quality Management Document			
 WORLDWIDE CLINICAL TRIALS	Sponsor:	TB Alliance	
	Protocol Number:	Pa-824-CL-011	
STATISTICAL ANALYSIS PLAN – PHASE 1			

Figure Number	Figure Title	Validation Method	Shell Number (if repeat)
14.4.1	Mean Plasma Concentration-Time Profiles of Pretomanid for Panel 1 on Linear and Semi Logarithmic Scales		
14.4.2	Mean Plasma Concentration-Time Profiles of Pretomanid for Panel 2 on Linear and Semi Logarithmic Scales		
14.4.3	Mean Plasma Concentration-Time Profiles of Pretomanid for Treatment A (Panel 1 vs Panel 2) on Linear and Semi Logarithmic Scales		
14.4.4	Mean Plasma Concentration-Time Profiles of Pretomanid for Treatment B (Panel 1 vs Panel 2) on Linear and Semi Logarithmic Scales		
14.4.5	Mean Plasma Concentration-Time Profiles of Pretomanid for Treatment C (Panel 1 vs Panel 2) on Linear and Semi Logarithmic Scales		
14.4.6	Mean Plasma Concentration-Time Profiles of Pretomanid for Treatment D (Panel 1 vs Panel 2) on Linear and Semi Logarithmic Scales		

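### The pooled food-effect ANOVAs in SAP 6.10.2 leave out the subject effect, so the common food-effect interval is too narrow and the interaction test that gates it is too conservative

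*SAP*

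**What the plan says.** The main food-effect analysis in SAP 6.10.2 compares Panel 1 with Panel 2 separately for each treatment, with panel as the only fixed effect. Two further analyses follow, introduced with "For informational purposes, the food effect will also be evaluated using the following ANOVA models".

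- **Pool 1 (A and B) and pool 2 (B, C and D):** "the ANOVA model will include panel, treatment, and the panel by treatment interaction term as fixed effects to determine if the food effect differs". An interaction p-value of 0.05 or less is read as a difference in food effect.
- **If p exceeds 0.05:** the interaction is dropped. For pool 2, "an ANOVA model with panel and treatment as the fixed effects will be used to determine the common food effect for the dispersible tablets"; pool 1 has the same rule.

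No subject, sequence or period term appears in either step. Other models in the documents differ:

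- SAP 6.10.1, for B versus A within a panel, specifies a mixed model with "sequence, period, and treatment as fixed effects; and subject as random effect".
- Protocol 8.2, for the food effect, specifies a mixed model with "panel, sequence, period, treatment, and panel-by-treatment interaction as fixed effects; and participant as random effect".
- SAP Section 7 states: "No changes to the planned analyses have been identified".

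In the SAP Section 9 table list, the per-treatment comparisons are Table 14.4.5 ("Systemic Exposure of Pretomanid Among Treatments Comparing Panel 1 vs. Panel 2"), pool 1 is Table 14.4.8 ("Assessment of Food Effect Across 200 mg Treatments (A and B) on Log-Transformed PK Parameters") and pool 2 is Table 14.4.9.

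**The concern.** Every subject takes all four treatments within one panel, so the pooled models contain two or three values per subject. An ANOVA with only panel, treatment and their interaction treats 48 subjects as 96 or 144 independent observations.

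This causes two errors in opposite directions whenever values from the same subject are positively correlated:

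- Panel is a between-subject factor. Its standard error is understated, so the interval for the common food effect is too narrow.
- Panel-by-treatment is a within-subject contrast. Between-subject variance inflates its error term, so the test rejects too seldom.

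The errors compound. A weakened gate allows pooling more often, and the pooled estimate then carries an interval that under-covers. Food effect is a secondary objective. Tables 14.4.8 and 14.4.9 are the only planned outputs that test whether it differs between the 200-mg treatments or across the dispersible doses.

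**Working it through.** **Inputs from the documents.** 24 subjects per panel (SAP Section 4); T = 2 values per subject in A+B and T = 3 in B+C+D (SAP Table 1 and 6.10.2); interaction gate at 0.05 (6.10.2). The 90% interval level is taken from SAP 6.3.1, since 6.10.2 itself states none.

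**Inputs assumed.** The documents give no CV or correlation for these comparisons and no statistical basis for the sample size, so there is no planned figure to reproduce. I take intra-subject correlation ρ = 0.3, 0.5, 0.7, total CV 25–45% (log-variance ln(1+CV²)), equal variances and complete data.

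**Step 1: common food effect.** With n per panel and total log-variance σ², the ANOVA variance is 2σ²/(nT). The true variance is that multiplied by 1+(T−1)ρ. Hence

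true SE / ANOVA SE = √(1+(T−1)ρ)

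- A+B: √1.3, √1.5, √1.7 = 1.14, 1.22, 1.30
- B+C+D: √1.6, √2.0, √2.4 = 1.26, 1.41, 1.55

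The ANOVA's 90% t multiplier is 1.661 (93 df) for A+B and 1.656 (140 df) for B+C+D. Dividing by these ratios gives effective multipliers of 1.46, 1.36, 1.27 and 1.31, 1.17, 1.07. Normal coverage is then about 85, 82, 80% and 81, 76, 71%. It does not depend on CV.

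**Step 2: interaction gate.** The contrast has variance proportional to (1−ρ)σ², but the ANOVA uses σ² as its error. The test statistic therefore shrinks by about √(1−ρ) = 0.84, 0.71, 0.55. For A+B the critical value of about 1.99 acts like 2.37, 2.81, 3.62, which are two-sided tail areas of about 1.8%, 0.5% and 0.03%.

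**Step 3: simulation.** I simulated two panels of 24 with a random subject intercept and analysed each data set with the SAP ANOVA and with subject within panel. The rows without a subject effect are:

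| | ρ=0.3 | ρ=0.5 | ρ=0.7 |
|---|---|---|---|
| 90% CI coverage, A+B | 85% | 82% | 79% |
| 90% CI coverage, B+C+D | 81% | 76% | 71% |
| Size of 5% interaction test, A+B | 2.0% | 0.6% | <0.1% |
| Size of 5% interaction test, B+C+D | 1.5% | 0.3% | <0.1% |

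With a subject effect, coverage was 90% and size 5% throughout. Among data sets that pass the gate at ρ = 0.5, coverage without it was no better: 82% and 76%.

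**Step 4: power of the gate.** One treatment's food effect differs from the rest. Power is shown without versus with a subject effect, at ρ = 0.5:

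| Difference, CV | A+B | B+C+D |
|---|---|---|
| 1.25-fold, 35% | 31% vs 61% | 25% vs 64% |
| 1.5-fold, 35% | 90% vs 98% | 92% vs 99% |
| 1.5-fold, 45% | 68% vs 90% | 65% vs 92% |
| 2-fold, 35% | 100% vs 100% | 100% vs 100% |

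The loss depends on ρ. For A+B at CV 35% and 1.25-fold it is 34% vs 47% at ρ = 0.3 and 26% vs 82% at ρ = 0.7. For a 2-fold difference, power is at least 99% in every scenario with CV 25–45%.

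**Step 5: effect on a reported interval.** Protocol 1.2 puts fasted bioavailability at about half of fed at 200 mg, so take a common ratio of 2 at CV 35%, ρ = 0.5, where σ² = ln(1.1225) = 0.1156.

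- A+B: ANOVA SE = √(2×0.1156/48) = 0.0694, giving 2·exp(±1.661×0.0694) = 1.78–2.24. With subject, SE = 0.0694×1.225 = 0.0850 and t(46) = 1.679, giving 1.73–2.31.
- B+C+D: ANOVA SE = √(2×0.1156/72) = 0.0567, giving 1.82–2.20. With subject, SE = 0.0801, giving 1.75–2.29.

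**The case against.** **The text may be shorthand.** SAP 6.10.2 lists terms to be included and does not say they are the only ones. The protocol's model has a random participant, and Section 7 declares no change. The contrast with 6.10.1 is also less clean than it first looks: the power model for B, C and D there, given as a general form, shows no subject term either. That last point is correct, so the contrast rests on the A/B model and on the protocol. I still find the shorthand reading implausible. The SAP writes mixed model and random subject where it intends them, and here writes ANOVA with fixed effects only.

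**The consequence is small.** This largely stands. The models are labelled informational. Table 14.4.5 gives ungated per-treatment estimates from one value per subject, and no margin or decision in the documents depends on the pooled tables. The intervals in Step 5 would not change a reader's view of a two-fold effect. However, Table 14.4.5 does not test whether the food effect differs between treatments.

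**The sizes are assumed.** This also stands. Unequal variances across doses, or a graded dose effect, would change the B+C+D power figures. The direction of both errors needs only positive intra-subject correlation, which is the premise of a crossover.

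**Sequence and period add nothing shown here.** Agreed: neither was simulated. They are proposed only to match the protocol's model.

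**Conclusion.** The concern holds. Followed as written, the pooled analyses give a common food-effect interval based on a standard error too small by a factor of 1.14–1.30 (A+B) or 1.26–1.55 (B+C+D) for ρ from 0.3 to 0.7. The gating test is well below its nominal 5% size, and power for a 1.25-fold difference is roughly halved or worse at ρ = 0.5 and CV 35%. These sizes rest on the assumed ρ and CV, complete data and the 90% level inferred from SAP 6.3.1.

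The damage is limited to Tables 14.4.8 and 14.4.9: the precision reported there and any statement that the food effect is common across treatments. Large differences are still detected, and the per-treatment comparisons are valid on this point. Section 7 is inaccurate in declaring no change, because the protocol's food-effect model includes the participant effect that 6.10.2 drops. This should be fixed, but it does not threaten the primary objective.

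**What to change.** In both pooled models of SAP 6.10.2, add subject within panel as a random effect, and include sequence and period so that the model agrees with Protocol 8.2. Take the two interaction tests, and any common food effect with its interval, from that model. State the interval level explicitly. The per-treatment ANOVAs need no change for this defect. Record in SAP Section 7 any remaining departure from the protocol's food-effect model.

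The cost is a wording change and one random term in two model calls, plus the sequence and period terms; no new data are needed. The SAP supplement shows that the database has been locked, but SAP Section 6 leaves room for further analyses justified in the study report, so the corrected models can be reported that way. The price is a wider common-effect interval, with the standard error up by a factor of 1.14–1.55 for ρ of 0.3–0.7. That width is the correct one.

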### 2.2 Secondary Objectives

The secondary objectives of the study are as follows:

- To determine the food effect for each of the formulations.
- To assess the effect of dose on the bioavailability of the dispersible pediatric formulation under fed and fasted conditions.
- To evaluate the taste perception of the dispersible pediatric formulation under fed and fasted conditions.
- To evaluate the short-term safety and tolerability for each of the formulations under fed and fasted conditions.

QMD Ref: Worldwide-TMP-ST-006-4.0 Effective: 12Aug2019	Governing QMD: Worldwide-SOP-ST-001
Confidentiality Statement This document is the property of Worldwide Clinical Trials Inc. and may not be duplicated, copied, altered or removed from company without prior approval from Worldwide Quality Assurance or in compliance with Worldwide Standard Operating Procedures.	

Worldwide Clinical Trials Controlled Quality Management Document		
 WORLDWIDE CLINICAL TRIALS	Sponsor: Protocol Number:	TB Alliance Pa-824-CL-011
STATISTICAL ANALYSIS PLAN – PHASE 1		

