### **4 SAMPLE SIZE**

Two panels of healthy male and female subjects (24 subjects per panel) will be dosed in this study. The sample size is not based on statistical considerations. The number of subjects planned for enrollment is considered sufficient to achieve the study objectives.

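### SAP 6.10.2 reports one common food effect whenever the panel-by-treatment p-value exceeds 0.05, with no confidence interval on how far the food effects differ (minor)

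*SAP*

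**What the plan says.** One secondary objective is "To determine the food effect for each of the formulations" (SAP 2.2). SAP 6.10.2 first compares Panel 1 (fed) with Panel 2 (fasted) for each treatment separately. It then adds two models for information. In each, "the ANOVA model will include panel, treatment, and the panel by treatment interaction term as fixed effects". Model 1 uses treatments A and B; model 2 uses B, C and D.

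For model 1 the decision rule is "A p-value equal to or smaller than 0.05 for the panel by treatment interaction term indicates that the food effect differs between the treatments". In the other direction, "If the p-value is greater than 0.05 an ANOVA model with panel and treatment as the fixed effects will be used to determine the common" effect of food on A and B. Model 2 repeats the rule for the dispersible tablets. Neither model sets a margin for calling the effects common, and neither asks for an estimate or interval for the interaction. The results go to Tables 14.4.8 and 14.4.9.

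Protocol 8.2 plans something different: one mixed model with "panel, sequence, period, treatment, and panel-by-treatment interaction as fixed effects; and participant as random effect", comparing fed with fasted for each formulation and dose. It keeps the interaction and has no p-value step. SAP section 7 records no changes to the planned analyses.

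On size, SAP 4 says "Two panels of healthy male and female subjects (24 subjects per panel) will be dosed in this study" and "The sample size is not based on statistical considerations". Neither document gives a CV, a power or a detectable difference.

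**The concern.** The rule lets a non-significant test decide that a single food effect is reported. A p-value above 0.05 can mean that the food effects are alike, or that the data are too noisy to separate them. The rule cannot tell these apart, and it works the wrong way round: the noisier the data, the more often a common effect is reported. Adding a subject term would correct the error variance but would leave this logic in place.

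The stake is whether a reader of Tables 14.4.8 and 14.4.9 would believe that food acts equally on the adult and dispersible tablets, or equally across the dispersible doses. Food is not a small influence here. Protocol 1.2 puts fasted bioavailability at about half of fed at 200 mg, and protocol 1.3 bases paediatric development on matching exposure to that in adults.

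**Working it through.** The plan states no power or detectable difference, so there is no figure of its own to reproduce.

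**Inputs from the documents:** 24 subjects per panel (SAP 4); interaction threshold 0.05 (SAP 6.10.2).

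**Assumptions, not in the documents:** all 24 complete in each panel; log-normal data; within-subject CV 15-30%; between-subject CV 30% where it matters; a difference of interest of 1.25-fold between food effects, ln 1.25 = 0.2231.

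**Model 1 with a correct within-subject error term.** The interaction is the difference between panels in the mean of ln(B) − ln(A). With sw = √ln(1 + CV²), each subject's difference has SD √2·sw. So SE = sw·√(4/24) = 0.4082·sw, with 46 df and a two-sided 5% critical t of 2.013. Power comes from the non-central F with 1 and 46 df and non-centrality (0.2231/SE)². Period and sequence terms are ignored; they would lower power slightly.

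| Within-subject CV | sw | SE | 0.2231/SE | Power | Missed |
|---|---|---|---|---|---|
| 15% | 0.1492 | 0.0609 | 3.66 | 0.95 | 5% |
| 20% | 0.1980 | 0.0809 | 2.76 | 0.77 | 23% |
| 25% | 0.2462 | 0.1005 | 2.22 | 0.58 | 42% |
| 30% | 0.2936 | 0.1198 | 1.86 | 0.45 | 55% |

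Power reaches 80% at a CV of about 19.3%. Withdrawn subjects are not replaced (protocol 3 and 7.4). With 20 completers per panel, power is 0.90, 0.69, 0.51 and 0.38, so 10%, 31%, 49% and 62% are missed.

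**Model 2 with a correct error term.** The test has 2 and 92 df and non-centrality 24·Σf²/(2·sw²), where f are the centred log food effects. If the effects are evenly graded over a 1.25-fold range, Σf² = 0.2231²/2 = 0.0249, so at CV 20% the non-centrality is 24 × 0.0249/(2 × 0.0392) = 7.6 and power is 0.68. Over CV 15, 20, 25 and 30%, power is 0.91, 0.68, 0.48 and 0.36, so about 9%, 32%, 52% and 64% are missed.

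**What the common figure then means.** If the food effects of A and B differ 1.25-fold, the pooled ratio estimates their geometric mean, which is off by √1.25 = 1.12 for each treatment. By simulation, among trials where the difference is missed (within-subject CV 20-30%, between-subject CV 30%), the common 90% CI computed with a correct standard error covers either treatment's own food effect about 68-73% of the time. That figure depends on the between-subject CV: a smaller one narrows the CI around the average and lowers coverage.

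**Model 1 as listed, with no subject term.** At between-subject CV 30%, simulation gives 74%, 77%, 80% and 82% missed at within-subject CV 15, 20, 25 and 30%. The excess over the table comes from the error term, not from the gate.

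**What an interval would show.** The 90% CI on the ratio of food effects runs from the estimate divided by to the estimate multiplied by exp(1.679·SE). The factor is exp(1.679 × 0.0809) = 1.15 at CV 20% and exp(1.679 × 0.1198) = 1.22 at CV 30%.

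**The case against.** The case for leaving the text alone has several parts.

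- **The miss rate is conditional.** A reader might infer that the test often fails whatever the data. The documents do not support that: they give no CV, and at 15% only about 5% of 1.25-fold differences are missed. The 1.25-fold target is also an assumption. This stands, so the range must be quoted with the result.
- **The SAP never says that p > 0.05 proves equality.** This is correct. It says only that a small p indicates a difference and that otherwise a common effect will be determined. But the word *common*, reached through a test and with no interval beside it, invites that inference, and the plan offers nothing to check it against.
- **The information is largely available elsewhere.** A reader might infer that the food-effect objective rests on the pooled figures, or that model 1 is the only route to comparing formulations. Neither holds. Table 14.4.5 gives fed/fasted by treatment. Tables 14.4.3 and 14.4.4 give B/A in each panel, and (B/A fed)/(B/A fasted) equals the ratio of food effects, B over A. The panels are independent, so an interval can be derived. Tables 14.4.6 and 14.4.7 give the dose slope in each panel. This stands and limits the harm.
- **The effect is small and the models are informational.** A pooled ratio off by 1.12 is modest beside a food effect of about two-fold. This also stands.
- **The as-listed miss rates are borrowed.** The 74-82% figures arise mainly from the missing subject term, which is a separate matter. They should not be used to size this point.

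**Conclusion.** The point holds as a minor one. In both informational models a p-value above 0.05 is enough to drop the interaction and report a single food effect, with no interval on how much the effects differ, and protocol 8.2 contains no such gate. With a correct error term, the chance of passing a true 1.25-fold difference between A and B runs from about 5% to 55% as the assumed within-subject CV goes from 15% to 30%. Because the true CV is not stated, the rule's reliability cannot be judged from the plan. The consequence is confined to the common figures in Tables 14.4.8 and 14.4.9. The per-treatment food effects, and so the secondary objective, do not depend on the gate.

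**What to change.** In SAP 6.10.2, models 1 and 2:

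- Remove the p-value gate and keep the interaction p-value as descriptive only.
- Fit a model with subject as random effect, in line with protocol 8.2.
- Always report the ratio of food effects with its 90% CI (B/A in model 1; C/B and D/B in model 2), beside the per-treatment fed/fasted ratios.
- If a pooled ratio is shown, label it as an average across treatments and not as evidence that the food effect is the same.

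If the sponsor wants to claim a common effect, it should prespecify its own margin for that CI. A margin of 80.00-125.00% is only one option and has no basis in the documents. It is also demanding here: with identical food effects, model 1 would meet it in only about 72%, 41% and 16% of trials at within-subject CV 20, 25 and 30%.

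The cost is a wording change, a few extra contrasts for Tables 14.4.8 and 14.4.9, and a less simple summary statement. No new data are needed.
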